## APPENDIX 4. SOLICITED ADVERSE EVENT (AE) INTENSITY GRADING

Adverse Event	Age	Intensity Grade	Parameter
Pain at injection site	< 6 years of age	0: None	-
		1: Mild	Minor reaction to touch
		2: Moderate	Cries/protests on touch
		3: Severe	Cries when limb is moved/spontaneously painful
	≥ 6 years of age	0: None	-
		1: Mild	Any pain neither interfering with nor preventing normal every day activities
		2: Moderate	Painful when limb is moved and interferes with every day activities
		3: Severe	Significant pain at rest. Prevents normal every day activities
Redness * at injection site	All		Record greatest surface diameter in mm
Swelling at injection site	All		Record greatest surface diameter in mm
Fever **	All		Record temperature in °C/°F
Fatigue	≥ 6 years of age	0: Normal	-
		1: Mild	Fatigue that is easily tolerated
		2: Moderate	Fatigue that interferes with normal activity
		3: Severe	Fatigue that prevents normal activity
Gastrointestinal symptoms (nausea, vomiting, diarrhoea and/ or abdominal pain)	≥ 6 years of age	0: Normal	-
		1: Mild	Gastrointestinal symptoms that are easily tolerated
		2: Moderate	Gastrointestinal symptoms that interfere with normal activity
		3: Severe	Gastrointestinal symptoms that prevent normal activity
Headache	≥ 6 years of age	0: Normal	-
		1: Mild	Headache that is easily tolerated
		2: Moderate	Headache that interferes with normal activity
		3: Severe	Headache that prevents normal activity
Drowsiness		0: None	Behaviour as usual

Document: CHAD3-004-EBO-Z\_Interim\_Final\_SAP\_v2\_0

Author: PPD Version Number: 2.0 Version Date: 14JUN2017

Template No: CS\_TP\_BS016 – Revision 3

Reference: CS\_WI\_BS005

Effective Date: 01May2012

Copyright © 2012 Quintiles Transnational Corp. All rights reserved.

The contents of this document are confidential and proprietary to Quintiles Transnational Corp. Unauthorised use, disclosure or reproduction is strictly prohibited.

	< 6 years of age	1: Mild	Drowsiness easily tolerated
		2: Moderate	Drowsiness that interferes with normal activity
		3: Severe	Drowsiness that prevents normal activity
Irritability/Fussiness	< 6 years of age	0: None	Behaviour as usual
		1: Mild	Crying more than usual/no effect on normal activity
		2: Moderate	Crying more than usual/interferes with normal activity
		3: Severe	Crying that cannot be comforted/prevents normal activity
Loss of appetite	< 6 years of age	0: None	Appetite as usual
		1: Mild	Eating less than usual/no effect on normal activity
		2: Moderate	Eating less than usual/interferes with normal activity
		3: Severe	Not eating at all

\* In case it is not possible to determine the extent of redness on darkly pigmented skin, it will be reported as uninterpretable on the Diary Card and in eSource.

\*\* Fever is defined as temperature  $\geq 37.5^{\circ}\text{C}$  /  $99.5^{\circ}\text{F}$ . The preferred route for recording temperature in this study will be axillary.

The intensity of local vaccination site redness/swelling will be scored as follows:

Age	Intensity Grade	Diameter Measurement (mm)
1 to 5 years of age	0: None	-
	1: Mild	> 0 to $\leq 10$
	2: Moderate	> 10 to $\leq 30$
	3: Severe	> 30
6 to 12 years of age	0: None	-
	1: Mild	> 0 to $\leq 20$
	2: Moderate	> 20 to $\leq 50$
	3: Severe	> 50

Document: CHAD3-004-EBO-Z\_Interim\_Final\_SAP\_v2\_0

Author: PPD Version Number: 2.0 Version Date: 14JUN2017

Template No: CS\_TP\_BS016 – Revision 3  
Effective Date: 01May2012

Reference: CS\_WI\_BS005

Copyright © 2012 Quintiles Transnational Corp. All rights reserved.

The contents of this document are confidential and proprietary to Quintiles Transnational Corp. Unauthorised use, disclosure or reproduction is strictly prohibited.

13 to 17 years of age	0: None	$\leq 20$
	1: Mild	$> 20$ to $\leq 50$
	2: Moderate	$> 50$ to $\leq 100$
	3: Severe	$> 100$

The intensity of fever will be scored as follows:

Age	Intensity Grade	Temperature Reading (°C)
All	0: None	$< 37.5$
	1: Mild	$\geq 37.5$ to $\leq 38.5$
	2: Moderate	$> 38.5$ to $\leq 39.5$
	3: Severe	$> 39.5$

## APPENDIX 5. LABORATORY ASSESSMENTS

Category	Test	Reported Unit	Conversion Factor	SI Unit	Toxicity Grading
Haematology	Basophils	%	1	%	
	Basophils absolute	/mm 	0.001	10  /L	
	Eosinophils	%	1	%	
	Eosinophils absolute	/mm 	0.001	10  /L	
	Haemoglobin	g/dL	10	g/L	Haemoglobin

Document: CHAD3-004-EBO-Z\_Interim\_Final\_SAP\_v2\_0

Author: PPD Version Number: 2.0 Version Date: 14JUN2017

Template No: CS\_TP\_BS016 – Revision 3

Reference: CS\_WI\_BS005

Effective Date: 01May2012

Copyright © 2012 Quintiles Transnational Corp. All rights reserved.

The contents of this document are confidential and proprietary to Quintiles Transnational Corp. Unauthorised use, disclosure or reproduction is strictly prohibited.

	Lymphocytes	%	1	%	
	Lymphocytes absolute	/mm 	0.001	10  /L	
	Mean cell volume	fL	1	fL	
	Monocytes	%	1	%	
	Monocytes absolute	/mm 	0.001	10  /L	
	Neutrophils	%	1	%	
	Neutrophils absolute	/mm 	0.001	10  /L	
	Platelets	/mm 	0.001	10  /L	Platelets
	Red blood cells	/mm 	0.000001	10  /L	
	White blood cells	x10  /μL	0.001	10  /L	White blood cells - decrease
Biochemistry	Alanine aminotransferase	U/L	1	U/L	Alanine aminotransferase increase by factor
	Creatinine	umol/L	1	umol/L	Creatinine
		mg/dL	88.4	umol/L	

Document: CHAD3-004-EBO-Z\_Interim\_Final\_SAP\_v2\_0

Author: PPD Version Number: 2.0 Version Date: 14JUN2017

Template No: CS\_TP\_BS016 – Revision 3

Reference: CS\_WI\_BS005

Effective Date: 01May2012

Copyright © 2012 Quintiles Transnational Corp. All rights reserved.

The contents of this document are confidential and proprietary to Quintiles Transnational Corp. Unauthorised use, disclosure or reproduction is strictly prohibited.

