#### 15.4.1. DERIVATIONS

Based on the aforementioned variables, the following variables will be derived:

- Relative day:
  - o Calculated relative to Day 0 vaccination (refer to Section 6.1: Reference Start Date and Relative Day).
- Change from Baseline for results in System of International (SI) units (refer to Section 6.7.1: Change from Baseline).
- Derived decrease categories (%):
  - o  $\text{Change from Baseline} / \text{value at Baseline} \times 100$
- Toxicity grade for selected laboratory tests (refer to APPENDIX 6: Laboratory Toxicity Grading for derivation details).
  - o Maximum grade overall will also be derived as the highest post-vaccination toxicity grade across all post-baseline visits and time points.
- Reference range indicator based on the results in SI units.
  - o Low: Result < reference range lower limit.
  - o Normal: Result  $\geq$  reference range lower limit AND result  $\leq$  reference range upper limit. o High: Result > reference range upper limit.

For clinical laboratory results below or above the limit of quantification will be handled as follows:

- Assign as equal to the limit of quantification, for example '<x' will be assigned as x for analysis purposes. SI conversions can be applied to the derived result. In the listings the result will be presented as the SI value (after conversion) with the qualifier symbol concatenated, for example '<y' in SI unit.

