## APPENDIX 6. LABORATORY TOXICITY GRADING

Category	Test (Unit)	Age	Gender	Grade			
				1	2	3	4
Haematology	Haemoglobin (g/dL)	≤ 12 years of age	Both	7.5 to 8.49	6.5 to 7.49	5 to 6.49	< 5
		> 12 years of age	Male	10 to 10.9	9 to 9.9	8 to 8.9	< 8
			Female	8.5 to 9.4	7.5 to 8.4	6.5 to 7.4	< 6.5
	Platelets (x10  /μL)	≤ 12 years of age	Both	75 to 99.999	50 to 74.999	25 to 49.999	< 25
		> 12 years of age	Both	75 to 100	50 to 74.999	25 to 49.999	< 25
	White blood cells - decrease (x10  /μL)	≤ 12 years of age	Both	2.5 to 3.999	1.50 to 2.499	1 to 1.499	< 1
		> 12 years of age	Both	2 to 2.749	1.50 to 1.999	1 to 1.499	< 1
	Biochemistry	Creatinine (mg/dL)	≤ 12 years of age	Both	1.2 to 1.7	> 1.7 to 2.1	> 2.1 to 2.5
> 12 years of age			Both	1.5 to 1.7	> 1.7 to 2	> 2.0 to 2.5	> 2.5
		≤ 12 years of age	Both	1.1 to 2.5xULN	> 2.5 to 5.0xULN	> 5.0 to 10xULN	> 10xULN

Document: CHAD3-004-EBO-Z\_Interim\_Final\_SAP\_v2\_0

Author: PPD Version Number: 2.0 Version Date: 14JUN2017

Template No: CS\_TP\_BS016 – Revision 3

Reference: CS\_WI\_BS005

Effective Date: 01May2012

Copyright © 2012 Quintiles Transnational Corp. All rights reserved.

The contents of this document are confidential and proprietary to Quintiles Transnational Corp. Unauthorised use, disclosure or reproduction is strictly prohibited.

	Alanine aminotransferase increase by factor	> 12 years of age	Both	1.1 to 2.5xULN	> 2.5 to 5.0xULN	> 5.0 to 10xULN	> 10xULN
--	---	-------------------	------	----------------	------------------	-----------------	----------

ULN: Upper limit of the normal range.

Note: acceptable limits for eligibility and grading scale adapted from Division of AIDS table for grading severity of adult and pediatric adverse events December 2004; WHO Toxicity Grading Scale for Determining Severity of Adverse Events, February 2003; Toxicity Grading Scale for Healthy Adult and Adolescent Volunteers Enrolled in Preventive Vaccine Clinical Trials, Guidance for Industry, 2007.

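### SAP Appendix 5 gives white cells a reported unit of ×10³/µL and a factor of 0.001 to 10⁹/L; the two are incompatible and, applied as written, make SI values and absolute changes 1000-fold too low

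*SAP*

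**What the plan says.** SAP v2 Appendix 5 lists each laboratory test with its reported unit, conversion factor, SI unit and linked toxicity test. For white cells the reported unit is "White blood cells x10 3 /μL" and the row continues "0.001 10 9 /L White blood cells - decrease". The same row stands in SAP v1. Every other absolute count is reported per mm³: the five absolute differentials share the pattern "Platelets /mm 3 0.001 10 9 /L Platelets", and red cells read "Red blood cells /mm 3 0.000001 10 12 /L".

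SAP 15.4.1 defines "Change from Baseline for results in System of International (SI) units" and a "Reference range indicator based on the results in SI units". SAP 15.4 lists laboratory results in SI units and local reference ranges in SI units among the variables that arrive in the Data Management transfer. Appendix 6 states its white cell limits in the reported unit: "White blood cells - decrease (x10 3 /μL".

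Haematological laboratory abnormality is one of the primary endpoints (protocol 11.1, SAP 2.1.2).

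**The concern.** The row contradicts itself. The factor 0.001 is what the /mm³ rows need, and it stands beside a unit that is a thousand times larger. White cell summaries and changes from Baseline are to be reported in SI units, by group and again in the pooled analysis after ChAd3-EBO-Z. A programmer who follows the row literally would put wrong numbers into tables for a primary safety endpoint. The SAP also names no input for toxicity grading, so nothing in the text prevents a mis-scaled SI value from being graded.

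**Working it through.** **Inputs.** Units, factors and SI units come from SAP Appendix 5, and grade limits from Appendix 6. Volumes: 1 L = 10⁶ µL = 10⁶ mm³.

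**Formula.** Factor = (cells per litre in one reported unit) ÷ (cells per litre in one SI unit).

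**Rows that reproduce the plan's figure**
- Platelets and the five absolute differentials: 10⁶ ÷ 10⁹ = 0.001. Stated 0.001; agrees.
- Red cells: 10⁶ ÷ 10¹² = 0.000001. Stated 0.000001; agrees.

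**The white cell row**
- In ×10³/µL: (10³ × 10⁶) ÷ 10⁹ = 1. Stated 0.001, so the result is 1000-fold too low.
- If the reported unit were /mm³: 10⁶ ÷ 10⁹ = 0.001. The stated factor would then be right.

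**Values and changes, applying the row as written**
- 6.0 × 0.001 = 0.006, against a correct 6.0 × 10⁹/L.
- A fall from 6.0 to 3.5 becomes 0.0035 − 0.006 = −0.0025, against a correct −2.5.
- Percent change: −2.5 ÷ 6.0 = −41.7% either way, because the factor cancels.

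**Range flags.** The documents give no white cell reference range, so 4 to 10 is assumed for illustration.

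| Count (×10³/µL) | Correct flag | Result and range both × 0.001 | Only result × 0.001 |
|---|---|---|---|
| 3 | Low | Low | Low |
| 6 | Normal | Normal | Low |
| 12 | High | High | Low |

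**Grades, age 12 years or younger.** Grade 1 is 2.5 to 3.999 and Grade 4 is below 1, in ×10³/µL.
- In the stated unit: 3 is Grade 1; 6 and 12 are Grade 0.
- If the mis-scaled SI value were compared with these limits: 0.003, 0.006 and 0.012 are all below 1, so all are Grade 4.

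**Which value is graded?** The other rows show that neither column serves for every test.
- Platelets: 90,000/mm³ must become 90 (× 0.001) before the limit of 75 to 99.999 ×10³/µL can be applied. The number to be graded equals the SI number.
- Haemoglobin: 7.0 g/dL is Grade 2 at age 12 or younger, but its SI value of 70 g/L (× 10) lies above every limit. The number to be graded is the reported one.

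**The case against.** The strongest reply is that the row may never have touched an output. SI results and SI ranges both arrive from Data Management, and the SAP does not say that Appendix 5 drives that conversion. In 15.4.1 the analysis team is told that it may apply SI conversions only for values beyond a limit of quantification. The unit label may also be the slip: every other absolute count is per mm³, and with that unit 0.001 is correct and nothing changes. All of this stands. It limits the claim about outputs, but not the finding that the row is wrong as written. Appendix 5 is the only conversion table in these documents.

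A reader might infer that every white cell flag is wrong, with all children Low. That requires scaled results to be set against unscaled ranges, and the documents do not say this happens; one factor on both leaves every flag as it was.

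A reader might also infer that all children would be Grade 4. Appendix 6 gives its limits in its own units (×10³/µL, g/dL, mg/dL). Grading SI values throughout would also misgrade haemoglobin and creatinine, whose SI units are g/L and µmol/L. The evident intent is to grade in the units shown, and in those units the white cell grades survive. What remains is that the SAP does not say so, and platelets show that some conversion is needed before grading.

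The scope is narrow. The platelet row, which carries the thrombocytopenia signal, is correct. A common factor applies alike to both groups and so creates no spurious difference in direction between them.

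**Conclusion.** The white cell row in Appendix 5 is arithmetically wrong as written: its unit and its factor cannot both be right. This rests on unit conversion alone and is certain.

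The size of the effect is conditional. If 0.001 was applied to data in ×10³/µL, all SI white cell values and absolute changes are 1000-fold too low. Percent changes are intact. Flags are wrong only if the reference ranges were not scaled by the same factor, and grades only if the mis-scaled SI value was compared with the Appendix 6 limits. If the data were per mm³, no output is affected and only the label needs correcting. The documents do not settle which case holds, so they do not show that any output is in error. They do show a specification for a primary safety endpoint that must be corrected and checked.

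**What to change.** - In Appendix 5, either set the white cell factor to 1 for ×10³/µL, or correct the reported unit to /mm³ and keep 0.001.
- Confirm which was programmed, for results and for reference ranges, in the Data Management transfer and in the analysis programs.
- If 0.001 was applied to ×10³/µL data, rerun the white cell outputs, including the pooled ones.
- Add a sentence that Appendix 6 grading uses values expressed in the units shown there.

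The cost is one table cell, one sentence and a program check, with a rerun only if the check fails.

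Separately, and as a minor item, protocol Appendix C states the ALT eligibility limit in IU/mL in Table 27 and in IU/L in Table 25. The two must be reconciled. This adds no weight to the white cell point: SAP Appendix 5 carries ALT in U/L with factor 1, and Appendix 6 grades it by multiples of the upper limit of normal.

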## APPENDIX 6. LABORATORY TOXICITY GRADING

Category	Test (Unit)	Age	Gender	Grade			
				1	2	3	4
Haematology	Haemoglobin (g/dL)	≤ 12 years of age	Both	7.5 to 8.49	6.5 to 7.49	5 to 6.49	< 5
		> 12 years of age	Male	10 to 10.9	9 to 9.9	8 to 8.9	< 8
			Female	8.5 to 9.4	7.5 to 8.4	6.5 to 7.4	< 6.5
	Platelets (x10  /μL)	≤ 12 years of age	Both	75 to 99.999	50 to 74.999	25 to 49.999	< 25
		> 12 years of age	Both	75 to 100	50 to 74.999	25 to 49.999	< 25
	White blood cells - decrease (x10  /μL)	≤ 12 years of age	Both	2.5 to 3.999	1.50 to 2.499	1 to 1.499	< 1
		> 12 years of age	Both	2 to 2.749	1.50 to 1.999	1 to 1.499	< 1
	Biochemistry	Creatinine (mg/dL)	≤ 12 years of age	Both	1.2 to 1.7	> 1.7 to 2.1	> 2.1 to 2.5
> 12 years of age			Both	1.5 to 1.7	> 1.7 to 2	> 2.0 to 2.5	> 2.5
		≤ 12 years of age	Both	1.1 to 2.5xULN	> 2.5 to 5.0xULN	> 5.0 to 10xULN	> 10xULN

Document: CHAD3-004-EBO-Z\_Interim\_Final\_SAP\_v2\_0

Author: PPD Version Number: 2.0 Version Date: 14JUN2017

Template No: CS\_TP\_BS016 – Revision 3

Reference: CS\_WI\_BS005

Effective Date: 01May2012

Copyright © 2012 Quintiles Transnational Corp. All rights reserved.

The contents of this document are confidential and proprietary to Quintiles Transnational Corp. Unauthorised use, disclosure or reproduction is strictly prohibited.

	Alanine aminotransferase increase by factor	> 12 years of age	Both	1.1 to 2.5xULN	> 2.5 to 5.0xULN	> 5.0 to 10xULN	> 10xULN
--	---	-------------------	------	----------------	------------------	-----------------	----------

ULN: Upper limit of the normal range.

Note: acceptable limits for eligibility and grading scale adapted from Division of AIDS table for grading severity of adult and pediatric adverse events December 2004; WHO Toxicity Grading Scale for Determining Severity of Adverse Events, February 2003; Toxicity Grading Scale for Healthy Adult and Adolescent Volunteers Enrolled in Preventive Vaccine Clinical Trials, Guidance for Industry, 2007.

## APPENDIX 7. VITAL SIGNS ASSESSMENTS

Assessment	Unit
Temperature	C
Height	cm
Weight	kg
Heart rate	beats per minute
Respiratory rate	breaths per minute

Document: CHAD3-004-EBO-Z\_Interim\_Final\_SAP\_v2\_0

Author: PPD Version Number: 2.0 Version Date: 14JUN2017

Template No: CS\_TP\_BS016 – Revision 3  
Effective Date: 01May2012

Reference: CS\_WI\_BS005

Copyright © 2012 Quintiles Transnational Corp. All rights reserved.

The contents of this document are confidential and proprietary to Quintiles Transnational Corp. Unauthorised use, disclosure or reproduction is strictly prohibited.

## APPENDIX 8. PHYSICAL ASSESSMENTS

Assessment
Abdomen
Anorectal
Breast
Cardiovascular
Eyes/Ears/Nose/Throat
Genitalia
Head/Neck/Thyroid
Lymph nodes
Musculoskeletal
Neurological
Respiratory
Skin

Document: CHAD3-004-EBO-Z\_Interim\_Final\_SAP\_v2\_0

Author: PPD Version Number: 2.0 Version Date: 14JUN2017

Template No: CS\_TP\_BS016 – Revision 3  
Effective Date: 01May2012

Reference: CS\_WI\_BS005

Copyright © 2012 Quintiles Transnational Corp. All rights reserved.

The contents of this document are confidential and proprietary to Quintiles Transnational Corp. Unauthorised use, disclosure or reproduction is strictly prohibited.
